## PROTOCOL SYNOPSIS

Study Title	Proactive Outreach for Smoking Treatment (POST)
Funder	NIH/NIDA
Clinical Phase	N/A
Study Rationale	
The US Public Health Service (USPHS) designated tobacco dependence as a chronic disease. This is especially true for smokers with serious mental illness (SMI) who make more cessation attempts and are less successful sustaining long-term abstinence than the general population. There is a significant health disparity wherein individuals with SMI have a higher tobacco use prevalence and a greater risk for tobacco-related mortality than the general population. Chronic care models suggest chronic disease management requires a multidisciplinary care team to assess tobacco use, administer treatment, support patient self-management, and monitor progress. Proactive telephone outreach to smokers and brief provider interventions are two effective chronic disease management strategies. Community based mental health centers (CMHCs) are a primary treatment access point for many smokers with SMI. However, rates of intervention with smoking by CMHC providers are low. In order to implement the chronic care model for tobacco dependence for CMHCs, comprehensive implementation strategies are needed.

Study Objective(s)	
Primary
 
 
• To develop an implementation strategy to implement proactive tobacco cessation treatment into community mental health treatment settings
 
 
Secondary
 
 
• To test the effectiveness of the implementation strategy as well as the effectiveness of a proactive tobacco cessation treatment strategy.
 

Test Article(s) (If Applicable)	The study intervention combines provider intervention about tobacco (asking patients if they use tobacco, advising patients to quit, assessing willingness to quit, assisting with quitting via counseling or medication or referral for treatment, and arranging for follow-up), and proactive outreach (calling smokers in the health system and offering treatment).
Study Design	There are 3 studies proposed in the grant. The first study consists of qualitative interviews of leadership, clinical staff, and patients at two community mental health centers. The following two studies

---

	will be two sequential pilot tests of the implementation strategy in two community mental health centers.
Subject Population Key Criteria for Inclusion and Exclusion:	Participants will be patients and employees (leadership and clinical staff) at two community mental health centers in Minnesota. Inclusion criteria for employees are to be on staff at the two community mental health center recruitment sites. There are no exclusion criteria for employees. Patient inclusion criteria include being English-speaking, current smokers (>25 days/month), patients at the community mental health center. Patient exclusion criteria includes judged by community mental health as being unable to participate in research (due to cognitive impairment or any other reason), no access to a telephone, no access to an address at which they can receive mail.
Number Of Subjects	Total Number of Subjects: Study 1: 29; Study 2: 25 patients, 33 staff; study 3: 50 patients, 200 staff Total Number at Hennepin Healthcare: 0 Total Number of Sites: 2
Study Duration	For study 1, each subject's participation will last one day, the entire study will last 3 months For study 2, each patient subject's participation will last 3 months, staff participation will last 6 months, the entire study will last 6 months For study 3, each patient subject's participation will last 15 months, staff participation will last 12 months, the entire study will last 18 months
Study Phases Screening Intervention Follow-Up	Study 1 potential participants will be approached for a single time point consent and qualitative interview. Study 2 potential patient participants will be approached in person or via an information letter, interested participants will complete informed consent and a baseline survey, all participants will receive and outreach attempt and may choose to enroll in counseling, participants will complete a follow-up survey 3 months post-enrollment. Some participants will be selected to participate in qualitative interviews. Study 3: potential participants will be approached, interested participants will complete informed consent and a baseline survey. 3 months later, participants will complete a second baseline survey. Participants will receive 3 outreach attempts, 3 months apart. At each outreach, participants will be given the choice of whether to enroll in counseling. Participants will complete follow-up surveys at 6, 9, and 15 months post enrollment.

---

---

Efficacy Evaluations	Study 1: Qualitative interview, Study 2: surveys at baseline and 3 months post-implementation and qualitative interviews, Study 3: participation data, surveys at 6, 9, and 15 months post-enrollment and interviews at 15 months post-enrollment
Pharmacokinetic Evaluations	N/A
Safety Evaluations	Study 1 is only a qualitative interview. If safety concerns arise during the interview, they will be documented and submitted to the IRB.  Study 2 & 3: participants' mental health providers will be informed about their study participation. If participants note a worsening of their mental health symptoms, we will inform their providers, take appropriate clinical action if necessary, and evaluate whether this change is due to changes in their smoking, and report to the IRB as an adverse event.
Statistical And Analytic Plan	Interviews will be coded using deductive and inductive codes. We will then conduct a framework matrix analysis. We will summarize implementation data with respect to treatment delivery and utilization, and patient outcome data. For patient outcomes, we will explore the adjusted effects using a series of generalized linear mixed effects models adjusted for potential confounders, baseline values and clustering.
Data And Safety Monitoring Plan	DSMB

---

**Study 1: Stakeholder Interviews**

Procedures		Pre-enrollment	Enrollment/interview call (day 0)
Chart Review	Identify smokers	X	
	Obtain clearance from treatment team	X	
	Distribute study flyer to eligible participants	X	
In CMHC (or by telephone)	Consent		X
	Interview		X

## Study 2: Short Pilot

Procedures		Pre-implementation (day 0-day 60)	Enrollment (day 30-90)	Implementation (Day 60-180)	End of Implementation follow-up (day 150-180)
Organizational coaching	Online training	X			
	Readiness meeting	X			
	Coaching calls	X		X	
	In-person workshop	X			
Staff training	Online training	X			
	In-person workshop/role play	X			
	Learning community	X		X	
	Performance feedback			X	
Patient recruitment and enrollment	Identify smokers	X			
	Informed consent		X		
Intervention delivery	5 A's delivered at each visit			X	
	Proactive outreach			X	
	Telephone counseling			X	
Assessment	Pre-post training evaluations	X			
	After visit surveys			X	X
	Baseline survey		X		
	3-month follow-up survey/biochemical verification				X
	Stakeholder interviews				X

### Study 3: Full Length Pilot

Procedures		Enrollment/Baseline 1 (day 0-60)	Pre-implementation (day 60-90)	Baseline 2 (day 90-180)	Implementation (Day 120-300)	3-month follow-up (day 210-240)	6-month follow-up (day 300-330)	12-month follow-up (Day 390-420)
Organizational coaching	Online training		X					
	Readiness meeting		X					
	Coaching calls		X		X			
	In-person workshop		X					
	Sustainment meeting				X			
Staff training	Online training		X					
	In-person workshop/role play		X					
	Learning community		X		X			
	Performance Feedback				X			
Patient recruitment and enrollment	Identify smokers		X					
	Informed consent		X					
Intervention delivery	5 A's delivered at each visit				X			

Intervention delivery		Enrollment/Baseline 1 (day 0-60)	Pre-implementation (day 60-90)	Baseline 2 (day 90-180)	Implementation (Day 120-300)	3-month follow-up (day 210-240)	6-month follow-up (day 300-330)	12-month follow-up (Day 390-420)
	Proactive outreach counseling			X	X			
Assessment	Pre-post training evaluations	X						
	After visit surveys	X	X	X			X	
	Patient baseline surveys	X	X					
	Follow-up surveys				X	X	X	
	Biochemical verification						X	
	Stakeholder interviews						X	X

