### **4.2.3 Study procedures and visits study 3**

#### **Patients.**

Enrollment. Patients will provide written or electronic, informed consent. They will then complete a baseline survey. At the time of the provider training, they will complete a second baseline survey. Following the second baseline survey, the smoking cessation case manager will begin an outreach attempt (phone, text, or in person). During the outreach, they can elect to enroll in smoking cessation counseling and/or get help from the case manager to reach out to their providers to obtain smoking cessation medication. Outreach attempts will be repeated at 3 months, and 6 months following the second baseline survey.

Follow-up. Participants will complete additional follow-up surveys at 3, 6, and 12 months following the second baseline survey. Follow-up surveys will be completed by phone or via an online survey. Participants who report abstinence at the 12-month follow-up will be asked to complete a mailed or in-person CO test. 5-6 patients will participate in a qualitative interview.

Providers will receive a study fact sheet and baseline survey prior to the trainings. Completion of the baseline survey or attendance at the trainings or coaching calls will be considered consent to participate. Providers will complete a recorded, online training via Zoom or an in-person training regarding providing smoking cessation interventions to patients. This training will be attended by investigators from Brown University ([name], [name]) who will edit training videos for future site use. Providers will then have the opportunity to participate in coaching calls for 9 months. Providers will receive performance feedback about smoking cessation interventions from patient surveys or electronic health record data starting at the second baseline through 9 months post implementation. Leadership for the organizations have already agreed to participate. Leaders will participate in a virtual or in person site visit at the beginning of the study. 5-6 employees will participate in a qualitative interview. We will work with the site to create the following implementation tools: handouts about community smoking cessation resources, handouts about smoking cessation medications, decision aids to complete the 5 As, templated language to put in electronic health record notes.

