## 7.1 Primary Endpoint

For study 2, the primary end point is 3 months post-implementation. For study 3, the primary end point is 12 months post-implementation (~15 months post-first baseline).

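### The Study 3 schedule places the 12-month follow-up at Day 390–420, only 8.9–9.9 months after the table's own launch day and before the primary time point falls due at the table's anchors

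*Combined protocol and SAP*

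**What the plan says.** The schedule table headed Study 3: Full Length Pilot gives enrolment and first baseline on Day 0–60 and a pre-implementation column, which holds the staff training, on Day 60–90. It then gives "Baseline 2 (day 90-180", "Implementation (Day 120-300", "3-month follow-up (day 210-240", "6-month follow-up (day 300-330" and "12-month follow-up (Day 390-420".

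The text defines the final time point in months:

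- Section 7.1: "For study 3, the primary end point is 12 months post-implementation (~15 months post-first baseline".
- Section 4.2.3 (Study 3 procedures): "Participants will complete additional follow-up surveys at 3, 6, and 12 months following the second baseline survey". Section 6.2 uses the same anchor for CO-confirmed 7-day abstinence.
- Section 6, Implementation measures: 12 months from the start of implementation.
- Synopsis (Study Phases and Efficacy Evaluations): a last survey 15 months after enrolment. Section 4.3.1 gives 15 months of patient participation.

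The synopsis puts second baseline three months after the first. Section 4.2.3 puts it at provider training, with outreach repeated 3 and 6 months after it. Section 4.2.3 also ties biochemical verification to the final visit: "Participants who report abstinence at the 12-month follow-up will be asked to complete a mailed or in-person CO test".

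**The concern.** Two of the three follow-up headers agree with the table's launch day and the third does not. The '12-month' window opens 90 days after the '6-month' window opens, where six months should separate them.

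The misdated column carries the Study 3 primary time point and, through section 4.2.3, the CO test. The table is the only place in the protocol that turns this visit into days. If staff book from it, abstinence reported as 12-month would be measured early and nearer to the last outreach contact than the text implies. A visit made at the wrong time cannot be moved afterwards.

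**Working it through.** **Inputs.** From the Study 3 table: enrolment Day 0–60, training Day 60–90, Baseline 2 Day 90–180, launch Day 120, follow-up windows as quoted. From the text: 12 months from launch or from second baseline, and 15 months from enrolment. One month is taken as 30.44 days, so 6, 12 and 15 months are 183, 365 and 457 days. Thirty-day months are shown where they matter. Only column headers are used, not the marks in the body of the table.

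**Step 1: reproduce the table's labels from launch.**

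- 3-month: 210 − 120 = 90 days (3.0 months). Reproduces.
- 6-month: 300 − 120 = 180 days (5.9 months; exactly 6 thirty-day months). Reproduces.
- 12-month: 390 − 120 = 270 and 420 − 120 = 300 days (8.9–9.9 months). Does not reproduce.

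**Step 2: find the due day under each anchor.** For launch, a 30-day window is compared with the table's window. For the other anchors, the smallest shortfall is the earliest due day minus 420, and the largest is the latest due day minus 390.

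| Anchor | Due day | Shortfall (days) |
|---|---|---|
| Launch, Day 120, + 12 months | 120 + 365 = 485, window 485–515 (480–510 with 30-day months) | 485 − 390 = 95; 480 − 390 = 90 |
| Baseline 2 column, Day 90–180, + 12 months | 90 + 365 = 455 to 180 + 365 = 545 | 455 − 420 = 35 to 545 − 390 = 155 |
| Enrolment, Day 0–60, + 15 months | 0 + 457 = 457 to 60 + 457 = 517 | 457 − 420 = 37 to 517 − 390 = 127 |
| Second baseline at training, Day 60–90, + 12 months | 60 + 365 = 425 to 90 + 365 = 455 | 425 − 420 = 5 to 455 − 390 = 65 |

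On the training anchor with 30-day months, the earliest due day is 60 + 360 = Day 420, the last day of the window.

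**Step 3: work back from the window.** A patient who is to reach 12 months by Day 420 needs a second baseline by 420 − 365 = Day 55. That is 90 − 55 = 35 days before the Baseline 2 column opens.

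**Step 4: time since last outreach.** The last outreach is 6 months after second baseline. Over the whole Baseline 2 column that is 90 + 183 = Day 273 to 180 + 183 = Day 363. The table's visit then falls 390 − 363 = 27 to 420 − 273 = 147 days after it. A visit at 12 months would fall about 183 days after it.

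**The case against.** The strongest reply is that the text already settles the timing. Sections 4.2.3, 6.2, 7.1 and 4.3.1 and the synopsis point to the same visit, 12 months after second baseline or launch and about 15 months after enrolment. Harm arises only if staff book from the table, whose columns mix site milestones with patient visits and may be partly a project timeline. Study 3 is also a single-group pilot of 50 patients. Its numerical success criteria in section 7 are feasibility and acceptability thresholds, and none rests on abstinence. All of this stands, and it lowers the severity. It does not make the header right.

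A reader might infer that the window precedes every possible definition of the primary time point. The documents do not support that without qualification. Section 4.2.3 puts second baseline at provider training, which the table places on Day 60–90. With 30-day months, the earliest such patient is due on Day 420 exactly. That reading only touches the edge of the window, and it conflicts with the table's Baseline 2 column, which opens on Day 90.

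Twelve months from first baseline (Day 360–420 with 30-day months) would also fit better. No section defines the end point that way, and the 3- and 6-month headers do not fit that anchor.

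A reader might also infer that the abstinence result will be biased. All participants receive the intervention, so the error cannot fall differently on two arms, and nothing in the documents fixes the size or direction of any effect.

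**Conclusion.** The header is wrong as written and should be corrected, but it does not undermine the design. Day 390–420 is 8.9–9.9 months after the table's launch day, and it closes before the primary time point at the table's own launch, Baseline 2 and enrolment anchors. There is no single shortfall: it runs from 5 days (training anchor, earliest patient) to 155 days (latest second baseline in the column), and is 90–95 days on the launch anchor that reproduces the other two headers.

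This rests on reading the table's days as one study clock and on taking 'post-implementation' in section 7.1 as counted from launch, which its 15-month gloss supports. Counting from the end of implementation on Day 300 would widen the gap (300 + 365 = Day 665).

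Whether the column is a misdated 12-month visit or a mislabelled 9-month visit cannot be told from the documents. Day 390 is 9 thirty-day months after launch, so both are possible. Under either, the schedule lacks a correct window for the primary time point.

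**What to change.** The sponsor should confirm what the column was meant to be and make one of these changes:

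- Preferably, replace the day range with the definition already in sections 4.2.3 and 6.2, 12 months from each patient's second baseline, with a stated tolerance.
- Otherwise, set the header to about Day 485–515 on the launch anchor.
- If a 9-month visit was intended, relabel the column and add the 12-month window.

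The cost is one column header or one sentence. Either timing fits the stated 18-month study (about Day 548). The Day 485–515 window leaves 548 − 515 = 33 days. A second baseline as late as Day 180 is due on Day 545 and leaves only 3, so the tolerance should be set with that in mind. The sponsor should also reconcile whether second baseline falls at training or in the Day 90–180 column.

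Two separate items need their own reconciliation and are not part of this point: the visit times in section 4.1.4, which are counted from launch and end at 15 months, and the 180-day implementation column against the nine months of support described elsewhere.

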## 2 BACKGROUND INFORMATION AND RATIONALE

The US Public Health Service Clinical Practice Guideline (CPG) designates tobacco dependence a chronic disease because tobacco users require several interventions and make several quit attempts over their lifetimes. This is especially true for smokers with SMI, who make more quit attempts and have higher relapse rates than smokers without SMI. There is a significant health disparity among individuals with SMI wherein the smoking prevalence is between 44-66%. Individuals with SMI die 15-25 years earlier than those without, due, in large part (64%), to smoking-related disease. Despite similar motivation to quit, the smoking prevalence among individuals with mental illness is not declining, in contrast to general population declines. One explanation is that available treatments are not reaching smokers with SMI.

Chronic care management strategies are effective at reducing tobacco use. Chronic care management relies on population-based care to ensure that guideline-consistent interventions reach all patients. The chronic care model proposes four essential chronic disease management activities: (1) periodic review of patients' disease course and management, (2) help for patients to self-manage their disease, (3) interventions to optimize disease control, and (4) continuous follow-up of patient progress. Chronic care management requires a multidisciplinary team, including individuals with behavioral treatment skills. The CPG recommends using the 5A's approach for the management of tobacco use. Providers should Ask all patients' their smoking status at each visit, Advise smokers to quit, Assess willingness to quit, Assist patients in quitting, and Arrange for follow-up. "Ask" doubles the odds of abstinence, "Advise" increases abstinence by 30% and a 1-3 minute provider-delivered intervention increases patient abstinence rates by 40%.

Tobacco cessation pharmacotherapies are effective for smokers with SMI. Varenicline, bupropion and nicotine replacement therapy are efficacious for patients with schizophrenia, major depression and bipolar disorder. However, in 2009, black box warnings for varenicline and bupropion urged monitoring for worsening psychiatric symptoms. The warnings were removed after a randomized,

placebo-controlled, clinical trial in 4116 smokers with mental illness found no safety concerns of varenicline, bupropion or the nicotine patch. Dissemination of accurate information about cessation pharmacotherapy to mental health providers, who may be wary due to warnings or fear of worsening symptoms, is essential.

Tobacco cessation counseling is effective for smokers with SMI. Given high levels of dependence among smokers with SMI, and barriers to cessation success, intensive treatment including longer duration counseling is necessary. With regard to cessation counseling, pilot or observational studies with smokers with SMI have found promising effects of a range of provider interventions including brief intervention, motivational interviewing, group therapy focused on cessation or wellness, peer intervention, intensive individual counseling and face to face smoking cessation counseling + smoking cessation care coordination. Of these approaches, brief interventions by psychiatric providers are particularly appealing for under-resourced CMHCs.

Telephone counseling is an evidence-based treatment modality for smokers with SMI. Telephone counseling has broad reach and is inexpensive per user. Quitlines are available nationwide and cost ~\$1.69 per caller. Quitline counseling can help smokers with psychiatric diagnoses to quit, for example, 16% of Quitline callers with a psychiatric diagnosis were abstinent at 7 months post enrollment. However, quit rates for callers with psychiatric diagnoses were 20% lower than those without. Telephone counseling outcomes are improved with: mental health tailoring, when combined with care coordination with providers, or in-person group counseling. In one study, mental health tailored telephone counseling was as effective as face-to-face counseling and better attended. With sufficient dose and mental health tailoring, telephone cessation counseling is highly effective. Telephone counseling and care coordination could be added to brief provider interventions to provide patients with the intensity of treatment needed for smokers with SMI.

Community mental health centers (CMHCs) are an ideal venue to implement chronic care management for tobacco dependence. CMHCs were established by the Community Mental Health Center Act of 1963, which shifted SMI treatment into the community. CMHCs provide comprehensive mental health treatment, including medication management, case management and counseling. For patients with SMI, CMHCs could be a better place to implement proactive, chronic care management for tobacco dependence than primary care. CMHCs represent the primary treatment access point for SMI patients. They comprise a comprehensive treatment team including psychiatric prescribers, case managers, and counselors. Psychiatric prescribers see their patients more often than primary care providers and are better equipped to adjust psychiatric medications following cessation. Case managers can ensure patients fill smoking cessation prescriptions and maintain reliable telephone access for telephone counseling. Counselors can reinforce behavioral changes to promote abstinence. These supports are not always available in primary care. However, mental health providers have the lowest rates of intervention with tobacco use of any healthcare providers. Among psychiatrists, rates of intervention with tobacco use are declining. The administration of smoking cessation treatment is especially low in CMHCs (only 30% of providers discuss smoking with at least half their patients annually and providers report low confidence in providing cessation interventions). Provider barriers include: undervaluing tobacco addiction as a problem, lack of knowledge of evidence-based treatment, lack of self-efficacy to change patient behavior, competing priorities, and required cross-discipline collaboration.

Implementing smoking cessation treatments that adhere to a proactive, chronic care model, requires a comprehensive implementation strategy that addresses provider and organizational barriers. In other treatment settings, strategies that have been effective in implementing tobacco cessation programs include provider education, performance tracking and feedback, clinical reminders, note templates, and incentives for meeting performance goals. Multi-modal strategies are more effective than single strategies.

Scant research has studied effective strategies to promote the implementation of comprehensive smoking cessation treatment among behavioral health providers. A pre-post knowledge test showed increased knowledge of smoking cessation treatment following a mental health provider training

program. A pilot implementation trial (N=304) in 6 CMHCs increased mental health providers' use of the 5 As for tobacco cessation. This implementation strategy included didactic training (for both staff and psychiatrists) and access to ongoing external coaching from a physician clinic liaison. This strategy was associated with a significant increase in patient receipt of 5A's at the 6- and 12-month follow-up assessments, and increased smoking abstinence rates among patients at the 12-month follow-up. Another model, the Addressing Tobacco Use Through Organizational Change Model (ATTOC) has shown promise in substance use treatment facilities. This model includes: a 3-day on-site consultation, 3-day off site staff training, identification and training of tobacco treatment specialists, and ongoing phone consultation for 6 months. Following implementation, ATTOC resulted in more favorable staff and patient beliefs toward tobacco dependence treatment, increased utilization of nicotine replacement therapy and increased receipt of smoking cessation counseling during the substance abuse treatment program. Finally a pre-post trial of academic detailing and decision support resulted in increased smoking cessation medication prescriptions and a decreased population smoking rate.

There are several limitations of prior implementation approaches with regard to promoting the implementation of tobacco use chronic care models in CMHCs. First, the ATTOC model requires an initial 3-day on-site consultation as well as extensive off-site training for tobacco treatment specialists: this level of training may be difficult for resource constrained CMHCs. Second, no prior implementation approaches have included ongoing performance feedback on the agency's implementation process. Multiple experimental studies have supported didactic training combined with ongoing performance feedback and coaching as the most effective staff training approach, relative to self-study or selected components (e.g., didactic training only, didactic + feedback, didactic + coaching). Third, prior implementation strategies have been tailored to specific types of providers such as mental health specialists or substance use treatment providers. A chronic care model requires use of a multidisciplinary team, suggesting that the implementation strategy needs to be flexible enough to meet the needs of a variety of stakeholders (i.e., psychiatrists, case managers, social workers, etc.). Fourth, because only one previous pilot study has tested the effect of an implementation strategy on patient outcomes, the effects of the prior implementation strategies on smoking cessation in psychiatric patients are not well understood. Finally, the focus of prior implementation strategies has been on early phases of the implementation process (i.e., preparation and implementation), with less of an explicit focus on strategies to promote long-term sustainment. Thus, implementation strategies are needed that can be adapted for low resource settings and multidisciplinary teams, that consider both implementation and patient outcomes, and that include performance feedback and strategies to promote sustainment.

To build upon the implementation strategies in prior studies, we have partnered with the New England Addiction Technology Transfer Center (ATTC), one of 14 SAMHSA funded regional centers charged with training front-line behavioral health treatment providers in evidence-based practice (of which Co-I [name] is director). The New England ATTC developed a comprehensive, theory-driven implementation strategy called the Science to Service Laboratory (SSL), which consists of three key components based on the extensive research on staff training: 1) didactic training, 2) performance feedback, and 3) coaching. A robust body of experimental literature has demonstrated that the combination of these three specific strategies is an effective implementation approach, and is more effective than any of the elements in isolation. Each component of the SSL is sufficiently flexible that it can be tailored to meet specific contextual factors, while retaining core features. For instance, with regard to performance feedback, the approach requires that providers receive external, ongoing feedback on their delivery of the target evidence-based intervention. However, the content, duration, frequency, and delivery model of specific performance feedback sessions can be tailored to meet the needs of different stakeholders and settings. There is a substantial literature demonstrating that performance feedback improves provider behavior. Feedback is most effective when: it is delivered by someone of influence, includes goals and action plans, it focuses on a problem where there is room for improvement, and recipients are non-physicians. The SSL has been rolled out in 5 states

in New England to help agencies implement evidence-based interventions, and staff have reported satisfaction with the approach. Additionally, Co-I [name] and colleagues found that substance use treatment agencies that received the SSL had 3.6 times greater odds of adopting an evidence-based substance use intervention (i.e., contingency management) than agencies that received training as usual (Preliminary study 5). The proposed study will be the first to adapt the SSL model to promote the implementation of a comprehensive smoking cessation intervention and to meet the unique needs of CMHCs. Despite being widely used, the SSL has been completely untested outside of specialty addiction settings. The proposed study will tailor the SSL to make it maximally beneficial. Results can easily be fed back into ATTC with great benefit.

